### **9.2.1 Actions Taken as a Consequence of an AE**

*Action taken with trial treatment:* Any action taken with trial medication as a consequence of the AE must be recorded (dose not changed, dose reduced, dose increased, drug interrupted, drug withdrawn, not applicable, unknown).

*Other action taken:* Any other action taken as a result of the AE must be recorded (none, concomitant medication, concurrent procedure).

*Withdrawn due to AE:* It must be recorded whether the AE leads to withdrawal from the trial.

### **9.3 Additional Reporting Requirements for Serious Adverse Events**

Any SAE must be reported to LEO on the (paper) SAE Form – Clinical Trials within 24 hours of first knowledge. This report should contain an assessment of available information on seriousness, severity, causal relationship to the IP or trial procedure, the action taken, the outcome to date, and a narrative description of the course of the event.

Any LSR classified as an SAE must be added to the AE form and in addition reported to LEO on the SAE form.

The completed SAE form must be scanned and e-mailed to the local safety contact person of LEO Entity using the following e-mail address [[contact]](mailto:[contact]) stating the following reference in the e-mail subject field: “PV report – IIS-PICATO-1386”.

It may be relevant for the (sub)investigator to enclose other information with the SAE form, such as reports of diagnostic procedures, hospital records, autopsy reports, etc.

Additionally, LEO may request further information in order to fully assess the SAE. The (sub)investigator must forward such information to LEO upon request by e-mail (see contact details above).

The investigator must notify the local Institutional Review Boards (IRBs)/Independent Ethics Committees (IECs) of SAEs as required by current applicable legislation for the concerned country, however no later than fifteen (15) days after becoming aware of the case.

In addition, the Sponsor shall forward to the LEO local safety contact person any received customer complaints related to any LEO produce, and ensure that all Adverse Events and customer complaints are described in the Final Report.

Causally related SAEs occurring after the completion of the clinical trial including any protocol required post-treatment follow-up period should not be routinely sought or collected. However, such events should be reported to LEO ([[contact]](mailto:[contact])) if the (sub)investigator becomes aware of them.

### **9.4 Follow-up for Final Outcome of Adverse Events**

During the trial, the investigator should follow up for final outcome on all AEs (including SAEs). Once a subject has completed the clinical trial, LSRs as well as AEs classified as possibly or probably related to

the IP, that are deemed clinically significant, should be followed for 2 months or until final outcome has been established, whichever comes first.

SAEs must be followed up until a final outcome has been established, i.e. the follow-up may continue beyond the end of the clinical trial.

## **10 Investigational Products**

### **10.1 Instructions to be Followed by Study Staff**

The following guidelines should be followed by the study staff when instructing the subjects on how to apply trial medication:

1. Ensure the subject follows the trial medication application guidance provided (see Section 10.2).
2. Ensure the treatment area has been marked on the study transparency with a permanent ink marker using the three-point landmark technique (see Appendix 1: Identifying and Documenting the Treatment Area).
3. Ensure that the treatment area has been sufficiently marked on the skin to assist with identification of the treatment area for subsequent applications.
4. Ensure the subject understands that a cotton swab should be used to apply trial medication and hands should be washed immediately after application. Contact with skin other than the treatment area must be avoided.
5. Ensure the subject understands that the trial medication must be stored in the refrigerator at home.
6. Ensure the subject is instructed to return all dispensed tubes to the site at Visit 2, 6 and/or 10 (Week 1, 5 and/or 9).
7. Ensure that the subject is provided with a Patient Safety and Study Instruction Sheet.

### **10.2 Trial Medication Application**

During each application (once nightly for 3 consecutive nights) a thin and wet layer of trial medication should be applied evenly on the treatment area.

Face: Exclude the nares, periorbital and perioral regions. For subjects with a beard, the amount applied should be reduced proportionally to the size of the beard.

Trunk: Include the buttock and genital regions. Exclude the neck.

Trial medication should not be applied in the beard. Subjects with sparse hair in the treatment area can be enrolled as long as the LSR and MC assessments are not compromised as judged by the (sub)investigator. For subjects with a beard, IP should be applied up to the line of the beard.

The forehead should be defined by the previous hairline and the lower part of the face should be defined by the jawline and the tip of the chin, respectively. The perioral region should be defined by the margins of the lips, and the periorbital region should be defined by the top of the eyebrows and the top of the

cheekbones, respectively. Trial medication should be applied to the nose from its upper part downwards, excluding the nares.

The following general treatment guidance should be noted:

- Subjects should not shave the treatment area during the treatment days.
- Trial medication should not be applied immediately after taking a shower and should be applied at least two hours before bedtime
- Subjects must avoid washing the treatment area or engaging in activities that cause excessive sweating for at least 6 hours following IP application
- When subjects resume their normal washing routine, they should wash the treatment area gently using a mild soap.
- Subjects should avoid use of non-medicated/non-irritant salves/emollients on the treatment area during treatment days. Subjects should wash the treatment area using a mild soap before starting use of salves/emollients.
- Subjects should avoid use of make-up and sunscreens on the treatment area until 15 days after last IP application. Note: Eye-make-up within the periorbital area and lipstick is allowed.
- Subjects should avoid occluding the treatment area with tightly fitting clothing, hairpiece or jewelry.
- Subjects should be advised not to allow other persons (including children) and pets to come into contact with the treatment area for a period of 6 hours following application.
- Subjects should avoid contact of IP with eyes.
- Subjects should avoid excessive sun exposure (e.g., sunbathing, tanning booths) and should wear protective clothing over the treatment area when exposed to sunlight.

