## 5 Trial Endpoints

### 5.1 Primary Endpoint

- Complete clearance at Week 4, defined as no clinically visible MCs in the treatment area

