### 7.3 Exclusion Criteria

1. Location of the treatment area
  - on the periorbital skin
  - within 5 cm of an incompletely healed wound
  - within 10 cm of a suspected basal cell carcinoma (BCC) or squamous cell carcinoma (SCC).
2. Previous participation in an ingenol mebutate trial.
3. Treatment with ingenol mebutate gel in the treatment area within 6 months or outside of the treatment area within 30 days prior to study treatment initiation.
4. Receipt of the following within 90 days prior to study treatment initiation:
  - interferons or interferon inducers
  - any dermatologic procedures or surgeries within the treatment area
5. Receipt of any topical prescription medications in the treatment area within 30 days prior to study treatment initiation.
6. Lesions in the treatment area have atypical clinical appearance (e.g. giant lesions greater than 5 mm, eczematous lesions, or folliculocentric lesions).
7. Active dermatologic conditions that may confound the diagnosis of MC or would interfere with assessment of treatment, such as scabies, cutaneous lymphoma, or psoriasis.
8. Clinical diagnosis/history or evidence of any medical condition that would expose a subject to an undue risk of a severe AE or interfere with assessments of safety and efficacy during the course of the trial, as determined by the (sub)investigator's clinical judgment.
9. Known history of infection with Human Immunodeficiency Virus (HIV).
10. History of melanoma.
11. History of chronic alcohol or drug abuse within 12 months prior to screening, or any condition associated with poor compliance as judged by the (sub)investigator.
12. Known or suspected allergy or reaction to any component of the IMP formulation.
13. Patients who have experienced a clinically important medical event within 90 days prior to study treatment initiation (e.g., stroke, myocardial infarction, etc).
14. Pregnant, breastfeeding, or lactating women.
15. Participation in any another interventional clinical trial within 30 days prior to study treatment initiation.

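### Section 10.2 forbids gel on the beard, nares and perioral region, but the treatment-area rules do not keep that skin out of the outline, so untreated lesions could count in the clearance endpoints

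*Protocol*

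**What the plan says.** **Where gel may go (Section 10.2).** Gel is to form an even layer over the treatment area. The section then sets limits: "Face: Exclude the nares, periorbital and perioral regions". For beards it gives three instructions: "Trial medication should not be applied in the beard"; "For subjects with a beard, IP should be applied up to the line of the beard"; and "the amount applied should be reduced proportionally to the size of the beard". Sparse hair in the area is acceptable if lesions and skin reactions can still be assessed.

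**Where the treatment area may be.** Section 7.2 (criterion 4) asks for at least 10 MCs in an area on the face and/or trunk, of at most 100 cm² in total. Section 7.3 (criterion 1) bars an area "on the periorbital skin", within 5 cm of an incompletely healed wound, or within 10 cm of a suspected basal or squamous cell carcinoma. Section 8.14 and the text of Appendix 1 describe how to draw and relocate the outline. Neither says to leave out skin on which Section 10.2 forbids gel.

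**What is counted.** Section 8.14 counts the visible, typical MCs in the treatment area. Complete clearance at Week 4 (Section 5.1) is "defined as no clinically visible MCs in the treatment area". Partial clearance and sustained clearance (Section 5.2) use the same area. Incomplete clearance in it at Week 4 or Week 8 leads to another three-night course (Section 6.1 and the footnotes to Section 8.1). None of these rules makes an exception for untreated skin.

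**The concern.** The protocol has one list of skin that must not receive gel and a shorter list of skin that must not be in the treatment area. Skin on the first list but not the second can be outlined, left untreated by instruction, and still counted.

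Complete clearance needs a count of zero, so a single such lesion can decide a subject's result. The same count decides retreatment, so a subject could be given further courses because of a lesion to which the protocol does not allow gel to be applied. Such lesions could also help a subject reach the entry minimum and would sit in the denominator for partial clearance. Section 5.2 has a separate endpoint for MCs outside the treatment area, and untreated lesions inside the outline blur that distinction.

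**Working it through.** The protocol states no figure on this point. The sample of 10 carries no stated response rate, alpha or power, so there is nothing to reproduce. The check compares the sections and then sizes the consequence.

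**1. The two lists compared**

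| Region | Gel forbidden (10.2) | Kept out of the treatment area (7.2, 7.3) |
|---|---|---|
| Periorbital | yes | yes, Section 7.3 |
| Nares | yes | not stated |
| Perioral | yes | not stated |
| Beard | yes | not stated |
| Neck | yes | yes in effect: only face and/or trunk qualify, 10.2 ends the face at the jawline and takes the neck out of the trunk |

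Three regions remain in which outlined and treated skin can differ: beard, nares and perioral.

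**2. Whether the text expects an overlap**

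If the outline already stopped at the beard line, an even layer over the outlined area would need no further adjustment for the beard. Reducing the amount according to the beard's size makes most sense if the nominal area includes some beard. This is strong for the beard. For the nares and perioral skin the case is only that nothing in the written rules prevents it.

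**3. Effect on the primary endpoint**

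Input: N = 10 (Section 6.2).

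- One result changed from success to failure: 1/10 = 10 percentage points.
- Example: 5/10 = 50% (exact 95% interval 18.7% to 81.3%) becomes 4/10 = 40% (12.2% to 73.8%).

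The result changes only if all treated lesions cleared and the untreated one persisted. Let p be the probability that a subject's treated lesions all clear by Week 4, and let m of the 10 subjects have an untreated lesion in the outline that persists to Week 4. Neither p nor m is in the protocol; both are assumed here. The expected observed rate is p × (10 − m)/10.

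| p | m = 0 | m = 1 | m = 2 | m = 3 |
|---|---|---|---|---|
| 30% | 30% | 27% | 24% | 21% |
| 50% | 50% | 45% | 40% | 35% |
| 70% | 70% | 63% | 56% | 49% |

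So the expected loss per affected subject is 10 × p points: 3, 5 or 7 points at these values of p.

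**4. Effect on entry and partial clearance**

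Illustration: a subject enters with exactly 10 MCs in the outline, 2 of them on skin that receives no gel. Only 10 − 2 = 8 lesions are treated, yet the entry minimum is met. Partial clearance needs 50% of 10 = 5 lesions gone. If the 2 untreated lesions persist, 5 of the 8 treated lesions must clear, which is 5/8 = 62.5% of them.

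**5. Effect on retreatment**

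If the untreated lesion is the only one left at Week 4 and again at Week 8, the rules lead to 2 further courses × 3 nights = 6 further applications.

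**The case against.** The best counter-argument is that Section 10.2 itself bounds the treatment area. Its trunk line, "Trunk: Include the buttock and genital regions. Exclude the neck", makes little sense as a nightly coverage instruction for an area of at most 100 cm², but good sense as a definition of which skin counts as trunk. The facial limits can be read the same way. The investigator draws the outline, and Section 10.1 makes the same staff responsible for compliance with 10.2 and for marking the area. Nothing tells them to outline skin that will go untreated. On the beard, stopping at its line makes it an edge, the sparse-hair sentence suggests dense hair is not expected inside, and the reduced amount may simply reflect a smaller treated surface. Only visible MCs count. The Appendix 1 figures are not available and may show limits.

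This reading is possible, and many investigators would probably draw the outline that way. But the protocol does not say so. The reading does not explain why Section 7.3 names only one of the facial regions in 10.2, nor why the amount depends on the beard's size.

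Other parts of the objection stand. The perioral region is small: "The perioral region should be defined by the margins of the lips". A reader might also infer four stronger points, none of which the protocol supports:

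- *The neck is affected too.* It is already outside both face and trunk.
- *Periorbital skin is the only location barred.* Section 7.3 also bars areas near unhealed wounds and suspected tumours.
- *The primary endpoint becomes unattainable for an affected subject.* Section 5.2 has an endpoint for clearance outside the treatment area, so the protocol itself allows that untreated lesions may clear.
- *Every affected subject costs 10 points.* That holds only where everything treated has cleared and the untreated lesion persists.

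**Conclusion.** The point holds for the beard and, on the wording alone, for the nares and perioral region. The protocol does not ensure that the skin outlined, treated and counted is the same. Where they differ, the error in complete clearance runs only downwards: 10 percentage points for each subject whose result changes, with up to two further courses for that subject.

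This rests on three conditions: a facial outline that includes skin barred from gel, a visible MC on that skin that persists, and clearance of all treated lesions. The protocol gives no basis for estimating how often they would coincide. Trunk-only areas are unaffected. The trial is a 10-subject case series with no stated success threshold, so severity is minor. It is still worth correcting, because the remedy is a matter of wording and the same count drives both the primary endpoint and retreatment.

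**What to change.** Reconcile Sections 7.2 (criterion 4), 7.3 (criterion 1), 8.14 and 10.2 and Appendix 1 so that the skin outlined on the transparency, the skin treated and the skin counted are the same. Section 8.14 already describes the transparency as a means of relocating the area to assess the skin that was treated, so this follows the protocol's own intent. Specifically:

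- State in Section 8.14 and Appendix 1 that the outline leaves out any skin to which the protocol does not allow gel to be applied, and refer to this from Sections 7.2 and 7.3.
- State that the entry minimum of 10 and all later in-area counts use only the outlined skin so defined, and that MCs on omitted skin are counted as outside the treatment area.
- Reconcile the beard sentences in Section 10.2 with that definition.

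Which skin may be treated is for the sponsor to decide; the request is only that the sections agree.

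The cost is a short wording amendment. A few subjects may need a differently placed area to reach 10 MCs.

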### **10.3 Precaution/Over Dosage**

#### **10.3.1 Skin Exposure**

The most common LSRs reported in previous clinical studies using Picato are erythema, flaking/scaling, and crusting. Less common LSRs include swelling/edema, vesiculation/pustulation, and erosion/ulceration. Completed clinical trials have shown LSRs to be transient and resolved within a couple of weeks.

In a low percentage of patients treated on face or scalp, swelling around the eyes or on the eyelids may develop to a point where it may be considered clinically significant. In such cases these AEs should be recorded as periorbital edema or eyelid edema. Treatment is usually straightforward with cold compress on the eye(s) with the subject resting in supine position for a few hours.

#### **10.3.2 Ocular Exposure**

If accidental eye exposure occurs, the eye should be irrigated immediately and extensively with water. The subject should immediately seek medical attention by contacting the investigator or other medically qualified healthcare professional (e.g., in an Emergency Room) for assessment and treatment. All treatments are to be administered at the discretion of the healthcare professional (in emergency room, ophthalmologist, and/or the investigator). Treatment with topical cycloplegic and topical ophthalmic antibiotics is recommended. Topical anti-inflammatory agents and eye pads may also be useful for patient comfort. The subject should be monitored closely in the first few days following exposure to check for

secondary infection and to assess visual acuity. Subjects should be warned that vision might worsen before improvement occurs.

Any suspected ocular exposure should be documented and brought to the attention of LEO.

### **10.3.3 Other Exposure**

Picato must not be ingested. If accidental ingestion occurs the subject should drink plenty of water.

## **10.4 Packaging of Investigational Products**

The IP will be delivered as commercial packages/bulk/filled containers needing filling and/or final labeling for clinical study use.

## **10.5 Storage of Investigational Products**

All LEO supplied drugs must be stored in a secure and restricted area under the conditions specified on the label and remain in the original container until dispensed.

At the site, the IP must be stored in a refrigerator at between 2°C and 8°C (36°F to 46°F). The refrigerator temperature must be monitored continuously and recorded. Do not freeze.

IP will be dispensed to the subjects at the site and will be applied at home. Subjects will be instructed to place the tubes in the home refrigerator as soon as possible. The tubes should be:

- stored sufficiently segregated from foodstuffs.
- stored safely to ensure against inadvertent exposure to non-participants (including children and pets).

## **10.6 Drug Accountability and Compliance Checks**

### **10.6.1 Drug Accountability**

The investigator is fully responsible for the IPs at the trial site and for maintaining adequate control of the IPs and for documenting all transactions with them.

The subject should return all dispensed IP, whether used or unused, at Visit 2, 6 and /or 10 (Week 1, 5 and/or 9). An inventory must be kept of the IP given to and returned by each subject treated in the trial. This inventory must be available for inspection by LEO, when necessary.

### **10.6.2 Trial Product Destruction or Return**

Any unused LEO supplied drugs must be destroyed or return as instructed by LEO Entity upon finalization of the study. If destroyed, documentation of such destruction must be provided to LEO Entity, at the latest together with the Final Report.

### **10.6.3 Treatment Compliance**

At Visit 2, 6 and/or 10, the subject should be asked how many tubes of IP were used and if she/he has used the IP as prescribed. Compliance/non-compliance and the reason for non-compliance must be recorded in the subject's trial records.

## **11. Ethics and Regulatory Authorities**

### **11.1 Institutional Review Boards (IRBs)/Independent Ethics Committees (IECs) and Regulatory Authorities**

Written approval or favorable opinion must be obtained from relevant IRB/IECs prior to the enrollment of subjects.

Any amendments to the approved clinical trial must be approved by/receive favorable opinion from relevant IRBs/IECs and regulatory authorities as required prior to the implementation.

The appropriate regulatory authority(ies) must be notified of/approve the clinical trial, as required.

### **11.2 Ethical Conduct of the Trial**

This clinical trial must be conducted in accordance with the principles of the revision current at the start of the trial of the World Medical Association (WMA), Declaration of Helsinki, Ethical Principles for Medical Research Involving Human Subjects.

### **11.3 Subject Information and Informed Consent**

All subjects shall receive written and verbal information concerning the clinical trial. This information will emphasize that participation in the clinical trial is voluntary and that the subject may withdraw from the clinical trial at any time and for any reason. All subjects will be given an opportunity to ask questions and will be given sufficient time to consider before consenting.

The subject's signed and dated informed consent to participate in the clinical trial must be obtained prior to any clinical trial related procedure being carried out in accordance with ICH GCP (4.8) and all applicable laws and regulations.

Subjects must be re-consented to the most current version of the ICF(s) during their participation in the trial.

A copy of the ICF(s) must be provided to the subject or the subject's legally authorized representative.

## **12 Progress and Final Reports**

The investigator is responsible for compiling and submitting progress reports to LEO at the end of each reporting period. Progress reports should describe the progress that has been made towards completion of the study, all relevant findings, any developments and the spend of the funding received from LEO. The progress reports should be submitted on a quarterly basis, calculated from the Effective Date.

The investigator is also responsible for compiling and submitting a final report to relevant authorities and LEO to provide an overview of the study in its entirety, including the findings. The final report should be submitted no later than six (6) months after the completion of the study or, in case of premature termination, thirty (30) days after the date of termination of the Agreement between LEO and the Sponsor.

Reports must be delivered by courier, certified mail, registered mail in writing, to the parties as follows:

LEO Pharma Inc.  
Attn.: [name], Medical Science Liaison  
[name]

With a copy to LEO Pharma A/S at:

LEO Pharma A/S  
Attn.: [name]  
[name]

